5.2 Specifics of Tests Performed During the Study

Described below are the specifics of the tests performed in this study.

5.2.1 ECOG Performance Status

The ECOG Performance Status scales (Oken et al 1982) will be used to assess how a patient's disease is progressing and assess how the disease affects the daily living abilities of the patient. These scales are listed in Table 5.2.1-1 (below). The higher the ECOG score, the worse the prognosis.

Comprehensive Cancer Center of Wake Forest University
A Pilot Study: Open-Label Clinical Trial of CPI-613 in Patients with Advanced Bile Duct
Cancers
CCCWFU # 59212

Table 5.2.1-1: Scales Used in ECOG Performance Status

Grade	ECOG
0	Fully active, able to carry on all pre-disease performance without restriction
1	Restricted in physically strenuous activity but ambulatory and able to carry out work of a light or sedentary nature, e.g., light house work, office work
2	Ambulatory and capable of all self-care but unable to carry out any work activities. Up and about more than 50% of waking hours
3	Capable of only limited self-care, confined to bed or chair more than 50% of waking hours
4	Completely disabled. Cannot carry on any self-care. Totally confined to bed or chair
5	Dead

5.2.2 Clinical Chemistry, Hematology and Coagulation

Clinical chemistry assessed includes:

glucose	BUN
creatinine	AST/serum glutamic-oxaloacetic transaminase (SGOT)
total protein	ALT/serum glutamic-pyruvic transaminase (SGPT)
albumin	alkaline phosphatase (ALP)
Na ⁺	total bilirubin
K ⁺	
Cl ⁻	
Mg	
Ca ⁺²	
PO ₄	
CO ₂	

Hematology includes:

complete blood count	hemoglobin
differential count	hematocrit
platelet count	

Coagulation includes:

Prothrombin time	Partial thromboplastin time
------------------	-----------------------------

Cardiac assessment includes:

Troponin I
ECG

Comprehensive Cancer Center of Wake Forest University
A Pilot Study: Open-Label Clinical Trial of CPI-613 in Patients with Advanced Bile Duct
Cancers
CCCWFU # 59212

5.2.3 Analyses of Plasma CPI-613 Concentrations, Possibly Metabolite Concentrations, and Possibly Other Analyses

Plasma samples for the determination of CPI-613 concentrations, possibly metabolite concentrations and possibly other analyses will be obtained before and at various times after dosing of CPI-613 on Day 1 of Pre-Cycle 1 & Day 1 of Cycle 1 at the following time points: ~5 min before dosing, and at 0.5, 1, 1.5, 2, and 4 hrs post-dose of CPI-613.

Blood (4 mL for each sample) should be obtained from a peripheral vein, and not from a central venous catheter. The blood samples should be collected in 4-mL lavender top collection tubes containing K2-EDTA anticoagulant. The procedures for obtaining plasma samples are described in subsequent sections.

The specific procedures for collecting the blood samples are:

Sample Collection:

1. Collect 4 mL of blood into K2-EDTA plasma tubes.
2. Blood samples should be processed within 30 minutes of collection and kept on ice or in an ice block until processing.
3. Turn the filled tube upside down and then return it to the upright position. Do this 8-10 times. Do not shake or vortex the tube. You can also place the tubes on a mechanical shaker for 10 minutes to ensure full mixing.
4. The samples are then immediately centrifuged (< 1300x g for 10 minutes). There should be ~2 mL of plasma from each 4 mL blood sample.
5. The plasma fraction should then be transferred in approximately equal fractions using a disposable pipette to two 1.8-mL Nunc cryovial (provided by Cornerstone) and immediately frozen. The total time from collection to freezing should not exceed 60 minutes. The recommended temperature for sample storage is -80°C (or lower).

Sample Tube Labeling

Each sample vial should be marked with a unique identifier, to be provided by Cornerstone. The unique identifier include the date and time of collection, dose, and subject number. A separate document (the “PK Sample Collection Log”) should then identify the number as it pertains to dosage, date, time of collection, etc.

Sample Tube Shipment

When all samples from each patient have been collected, they should be shipped to Cornerstone Pharmaceuticals, Inc., to the attention of [name].

Comprehensive Cancer Center of Wake Forest University
A Pilot Study: Open-Label Clinical Trial of CPI-613 in Patients with Advanced Bile Duct
Cancers
CCCWFU # 59212

Sample vials should be kept frozen during shipment through the use of dry ice. Boxes should contain 30-40% of the box volume in dry ice, or enough to keep the samples frozen for at least three days. Dry ice pellets, as opposed to a single slab of dry ice, are preferred and should surround the sample.

Samples should be shipped via priority overnight courier Monday, Tuesday or Wednesday to ensure arrival before the end of the business week. Do not ship during a holiday week or when severe weather is expected that may delay the shipment either at the final destination or transfer points.

Ensure that the total package weight does not exceed 27.2 kg (60 pounds). Notify the contract lab via email on the morning of the shipment day. The contract labs and the email addresses are:

Lab: Cornerstone Pharmaceuticals, Inc.
Email Address: [contact]

Documentation Accompanying Shipment

Each shipment should contain the following information on a document separate from the sample vials (the PK Sample Collection Log). The document should be placed in an envelope taped to the outside of the Styrofoam container but inside the outer cardboard box.

Also, send an email to give [name] Cornerstone Pharmaceuticals, Inc. notice that the shipment is coming. The email should provide the protocol number, number of insulated boxes being shipped, a scan of the PK Sample Collection Logs of the patient samples being shipped, the name of the express courier including the tracking number and the method of shipment (preferably FedEx Priority Overnight), and expected date and time of arrival, plus the contact information of the person at Wake Forest University Health Sciences who is responsible for the shipment.

Shipment Address

Samples should be shipped to:

[name]
Cornerstone Pharmaceuticals, Inc.
[name]
[name]
Office [contact] ext. 212
Mobile [contact] [contact]
Email: [contact]

CPI-613 and Metabolite Assays

Plasma concentrations of CPI-613 and possibly metabolites will be assayed

Comprehensive Cancer Center of Wake Forest University
A Pilot Study: Open-Label Clinical Trial of CPI-613 in Patients with Advanced Bile Duct
Cancers
CCCWFU # 59212

using the validated Liquid Chromatography (LC)-Mass Spectroscopy/Mass Spectroscopy (LC/MS/MS) method (Cornerstone Study# VLD-002). Individual and mean plasma concentrations of CPI-613 and possibly metabolites for each patient will be tabulated at each time point and presented graphically. The following parameters will be estimated in all patients (as appropriate) from individual plasma concentration vs. time data:

- the maximum observed concentration (C_{max})
- area under the curve from time zero until the last measurable concentration (AUC_{0-t} , calculated by the linear trapezoidal rule and extrapolated to infinity by acceptable methods)
- area under the curve from time zero to infinity ($AUC_{0-infinity}$)
- K_{el} (estimated by linear regression of the terminal elimination phase)
- $t_{1/2}$
- Cl
- V_d
- C_{end}

5.2.4 *Optional Sampling and “Banking” of Blood and Serum Samples*

Optional blood and serum samples (10 mL and 8.5 mL, respectively) will be obtained and “banked” for possible testing of biomarkers, predictors of biological responses, toxicity, relationship between genotype and drug responses, etc. These samples will be obtained prior to treatment initiation (within 4 weeks prior to 1st dose), as well as prior to each restaging scan.

Whole Blood Samples

- Samples (10 mL each) will be collected into a green top sodium heparin Vacutainer[®] tube.
- Invert the tube a minimum of 10 times to mix the anticoagulant (sodium heparin) completely, then place sample on crushed ice.
- Label sample and store at refrigerated temperature (2-8°C).
- Samples will be shipped on cold pack to the address shown at the bottom of this section within 24-48 hours.

Serum Samples

- Collect blood (8.5 mL each) in serum separator tube (10.0mL, with Polymer gel/Silica activator).
- Gently invert the tube 8-10 times, and let tube sit in an upright position for at least 15-30 minutes at room temperature to allow the blood to clot.
- Within 2 hours from time of collection while at room temperature, spin the tubes at 1000x g using a standard room temperature centrifuge for 10-15

Comprehensive Cancer Center of Wake Forest University
A Pilot Study: Open-Label Clinical Trial of CPI-613 in Patients with Advanced Bile Duct
Cancers
CCCWFU # 59212

- minutes.
- After centrifugation, pipette 1.0 mL aliquots of plasma into each of the 1.8 mL-size polypropylene screw-capped cryovials. Expect to collect between 3-5 cryovials each containing 1.0 mL aliquots of plasma.
 - Label the aliquots.
 - Quickly freeze the aliquots by placing them either on dry ice or in a -70°C freezer. Store the samples at -70°C or colder until shipment.
 - Samples will be shipped on dry ice to the address shown at the bottom of this section

Shipment of Optional Samples

All optional samples and specimens should be shipped to:

[name]
Cornerstone Pharmaceuticals, Inc.
[name]
[name]
[contact] ext.215
[contact]
Email: [contact]

Comprehensive Cancer Center of Wake Forest University
A Pilot Study: Open-Label Clinical Trial of CPI-613 in Patients with Advanced Bile Duct
Cancers
CCCWFU # 59212

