5.0 STUDY PROCEDURES

Table 5-1 (below) provides an overview of the study procedures for the pre-study screen and pre-cycle 1 treatment period. The specifics are described in subsequent sections.

Table 5-1: Study Procedures for Pre-Study Screen and Pre-Cycle 1 Treatment Period

Assessments	Pre-Study Screen ⁸	Pre-Cycle 1 treatment (Given Only Once for Each Patient)	
		Days 1-5	Days 6-7
CPI-613 ¹		√	
Medical history	√		
Pregnancy test for women of child-bearing potential	√		
Evaluation of symptoms and vital signs	√ ³	√ ⁴	
ECOG performance status and survival	√		
Clinical chemistry, hematology and coagulation ²	√	√ ⁵	
Cardiac: Troponin I	√	√ ⁵	
Cardiac: ECG	√	√ ⁵	
CT w/ contrast (chest/abdomen/pelvis)	√		
CA-19-9	√		
Plasma CPI-613 concentrations, possibly metabolite concentrations, and possibly other analyses ⁶		√ ⁷	
Optional blood and serum samples ⁹	√		
Adverse event evaluation		√	√

ECOG = Eastern Cooperative Oncology Group; hr = hour; min = minute.

¹ CPI-613 is given as a 2-hr IV infusion via a central venous catheter.

² Specific chemistries are listed in section 5.2.2. Renal function will be assessed utilizing the Cockcroft-Gault formula. Coagulation (PT/PTT) will only be assessed at screening.

³ Other than evaluation of symptoms and vital signs, height and weight, physical exam, and medications are also determined during pre-study medical screening.

⁴ Perform on Days 1 and 4 only.

⁵ Perform on Days 1 and 5 only.

⁶ Obtained according to the following schedule: pre-dose (~5 min before dosing), and at 0.5, 1, 1.5, 2, and 4 hrs post-dose of CPI-613.

⁷ Day 1 only

⁸ Pre-study screening tests, which are also enrollment evaluations, must be performed according the following time frames:

Within 4 weeks: tumor assessment (CT w/ contrast), CA-19-9

Within 2 weeks: medical history, physical exam, vital signs, height, weight, ECG, ECOG, evaluation of symptoms and medications, clinical chemistry, hematology, coagulation, and troponin

Within 1 week: pregnancy test for women of child-bearing potential, pre-study labs and ECG obtained before enrollment may be used for Day 1

⁹ Optional blood and serum samples are for possible testing of biomarkers, predictors of biological responses, toxicity, genotype vs. drug response relationship, etc.

Comprehensive Cancer Center of Wake Forest University
A Pilot Study: Open-Label Clinical Trial of CPI-613 in Patients with Advanced Bile Duct Cancers
CCCWFU # 59212

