Based on Phase I trials in patients with solid tumors and hematologic malignancies, 3,000 mg/m² is the MTD, when CPI-613 is given as a single agent infused over 2 hours on Days 1 and 4 for 3 weeks of a 4-week treatment cycle. CPI-613 did not induce any significant adverse effects at or below MTD. Additionally, CPI-613 at or below 3,000 mg exhibits anti-tumor activities in patients with various types of solid and hematologic malignancies (Pardee et al, 2011a and b, & 2012; Lee et al. 2011 & 2012; Senzer et al 2012). Because of the safety and efficacy against other cancers, 3,000 mg/m² is the target dose for this pilot study.

In this study, patients will be treated with CPI-613 for 5 consecutive days during pre-Cycle 1, prior to being treated with CPI-613 given 2x weekly for 3 weeks. A sub-MTD (2,300 mg/m², approx. three-quarters of the MTD) will be used in the first 3 patients (in Cohort 1) who will be treated with the 4-week treatment cycles and without treatment during the pre-Cycle 1 week to ensure safety, before initiating the dose escalation procedure to determine the MTD. The maximum plasma concentration (C_{max}) of CPI-613 associated with the dose level of 2,300 mg/m² is ~90 µM, which is significantly lower than the C_{max} of ~200 µM associated with 3,000 mg/m². Therefore, 2,300 mg/m² is expected to be a safe starting dose.

After determining the dose to be used in 3-weeks-on-1-week-off cycles, the safety of the dailyx5 treatment with CPI-613 during pre-Cycle 1 will be evaluated in a dose-escalated manner in Cohorts 2-4.

6.2 Dosing Delay and Dose Modification of CPI-613 in the Event of Adverse Events

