7.5 Reconstitution and Administration of CPI-613

CPI-613 must be diluted from 50 mg/mL to 12.5 mg/mL with 5% Dextrose Water or D5W (i.e., 1 portion of CPI-613 diluted with 3 portions of D5W) prior to administration. The diluted drug product should be visually inspected for clarity. If haziness, precipitate or coloration (other than colorless) is observed, do not use the diluted drug product for dosing. After dilution with sterile D5W, the solution is clear and has a pH of 8.4-8.8. The diluted CPI-613 drug product has been found to be stable for 24 hrs at room temperature and refrigeration temperature (Studies STA-010).

CPI-613 must be administered IV, via an IV catheter that is free flowing and free of air in the dead space of the IV catheter, to minimize vascular irritation, inflammation and acute toxicity of CPI-613 (Study NCL-049). Accidental co-administration of extra air in the dead space of IV catheters during administration of CPI-613 has demonstrated the potential to induce acute toxicity of CPI-613 according to animal studies (Study NCL-049). Also, accidental leakage of CPI-613 into the perivascular space during IV administration, which prolongs exposure of perivascular tissue to CPI-613, can induce significant local inflammation according to animal studies (Studies NCL-027 and NCL-030). To avoid local reactions at and around the site of administration, CPI-613 must be administered via a central venous catheter.

CPI-613 must not be administered as a bolus, but by infusion, at a rate of ~0.5 mL/min, via a central venous catheter with D5W running at a rate of about 125-150 mL/hr. This is to minimize potential acute toxicity of CPI-613, according to animal studies (Study NCL-049).

The following precautions must be taken when administering CPI-613:

- A. Confirmation of the placement of the IV line to ensure a lack of leakage of CPI-613 into the perivascular space.
- B. Confirmation that the IV line is free flowing.
- C. Confirmation that the IV line is free of dead air space.
- D. Dilute CPI-613 drug product with D5W, as instructed in the study protocol.
- E. Administer CPI-613 by infusion, not as a bolus.
- F. After administration of CPI-613, flush the IV line with ~10 mL of D5W to remove

Comprehensive Cancer Center of Wake Forest University
A Pilot Study: Open-Label Clinical Trial of CPI-613 in Patients with Advanced Bile Duct
Cancers
CCCWFU # 59212

residual CPI-613.

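### Section 5.2.3 applies the linear trapezoidal rule to the whole AUC0-t; if sampling times run from infusion start, this overstates AUC0-t, materially only if half-life is about 1 h or less

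*Combined protocol and SAP*

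**What the plan says.** The PK paragraph of Section 5.2.3 states that AUC0-t, up to the last measurable concentration, is "calculated by the linear trapezoidal rule" and "extrapolated to infinity by acceptable methods". It lists AUC0-infinity, K_el, t1/2, Cl and Vd as further parameters, with K_el "estimated by linear regression of the terminal elimination phase".

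Samples are taken "on Day 1 of Pre-Cycle 1 & Day 1 of Cycle 1", at about "5 min before dosing, and at 0.5, 1, 1.5, 2, and 4 hrs post-dose of CPI-613". Neither Section 5.2.3 nor the footnotes to Tables 5-1 and 5-2 say whether the post-dose clock starts at the beginning or the end of the infusion.

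On the infusion itself, the Table 5-1 footnote says "CPI-613 is given as a 2-hr IV infusion via a central venous catheter". Section 7.5 has the drug, diluted to 12.5 mg/mL, given "by infusion, at a rate of ~0.5 mL/min".

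The only PK results in the documents are two Cmax values in Section 6.1.2. No half-life, AUC or clearance is reported.

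**The concern.** Counted from the start of a 2-h infusion, the samples at 0.5, 1, 1.5 and 2 h follow the rise, and the 4-h sample is the only one after the infusion stops. The observed decline is then a single 2-h interval. A first-order decline is convex and lies below the chord joining its ends, so the linear rule overstates that interval whatever the half-life. The size depends on half-life, which nobody can read from the plan.

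At stake is the accuracy of a tabulated AUC0-t. It would be biased upward by the choice of rule when another rule, applied to the same samples, does better.

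**Working it through.** **Inputs.** 2-h infusion (Table 5-1, Section 6.0); samples at 0, 0.5, 1, 1.5, 2 and 4 h (Section 5.2.3), first taken as timed from infusion start; linear rule (Section 5.2.3). Half-life is an assumption. The plan states no AUC or bias figure, so there is none to reproduce.

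**Model.** One compartment, no assay error, k = ln 2 / t1/2. In arbitrary units C(t) = 1 − exp(−kt) up to 2 h, then C(2)·exp(−k(t − 2)). For the last interval, with x = 2k,

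linear / true = (x/2)(1 + e^−x) / (1 − e^−x).

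**Example, t1/2 = 1 h (k = 0.6931).** Concentrations are 0, 0.2929, 0.5000, 0.6464, 0.7500, 0.1875.

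- 0-2 h, linear: 0.5 × (0.2929 + 0.5000 + 0.6464 + 0.7500/2) = 0.9072. True: 2 − 0.75/0.6931 = 0.9180. Error −1.2%.
- 2-4 h, linear: 2 × (0.7500 + 0.1875)/2 = 0.9375. True: (0.7500 − 0.1875)/0.6931 = 0.8115. Error +15.5%.
- 0-4 h, linear: 0.9072 + 0.9375 = 1.8447, against 1.7295. Error +6.7%.
- 0-4 h, linear-up/log-down: 0.9072 + 0.8115 = 1.7187. Error −0.6%.
- Extrapolated part: 0.1875/0.6931 = 0.2705, which is 13.5% of the true AUC0-infinity of 2.0000.
- Clearance from the linear rule and the true K_el: 2.0000/(1.8447 + 0.2705) = 0.9455 of the true value, error −5.4%.

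The same steps over a range of assumed half-lives:

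| t1/2 (h) | 2-4 h interval, linear | AUC0-4h, linear | AUC0-4h, linear-up/log-down | Extrapolated share of AUC0-infinity | Cl, linear rule and true K_el |
|---|---|---|---|---|---|
| 0.5 | +57.1% | +17.1% | −1.4% | 2.1% | −14.4% |
| 1 | +15.5% | +6.7% | −0.6% | 13.5% | −5.4% |
| 2 | +4.0% | +2.0% | −0.3% | 36.1% | −1.2% |
| 4 | +1.0% | +0.5% | −0.1% | 59.8% | −0.2% |
| 8 | +0.3% | +0.1% | −0.1% | 77.2% | 0.0% |

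At 0.25 h the linear error reaches +29.3%. The 4-h value is then 2^−8 = 0.4% of the 2-h value and may not be measurable, in which case AUC0-t would stop at 2 h. That figure is an upper case.

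**With a distribution phase.** Seven two-compartment cases were run with times from infusion start (fast half-life 0.25 or 0.5 h, slow half-life 2 to 12 h, fast-phase coefficient 50% to 95%), taking K_el from the 2-h and 4-h samples.

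- AUC0-4h: linear +4.4% to +20.9%; linear-up/log-down +2.4% to +11.4%, and closer in every case.
- AUC0-infinity: linear −3.3% to −50.8%; linear-up/log-down −5.8% to −53.5%.
- Clearance with the linear rule: +3.4% to +103.2%. The estimated half-life was 0.85 to 2.14 h, always shorter than the true slow phase.

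**Times counted from infusion end.** The samples then fall 2.5, 3, 3.5, 4 and 6 h after the start, with none during infusion. For one compartment, linear AUC0-6h is too low by 52.1%, 27.7%, 15.0% and 9.6% at half-lives of 0.5, 1, 2 and 4 h. With the log rule the shortfalls are 53.9%, 29.6%, 15.9% and 9.9%.

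**Infusion duration against rate.** Volume = dose × BSA / 12.5 mg/mL. For an assumed BSA of 1.5 to 2.0 m², 1,200 mg/m² is 144 to 192 mL and 3,000 mg/m² is 360 to 480 mL. At 0.5 mL/min these take 4.8 to 6.4 h and 12 to 16 h. Timed from the start, every sample would then fall during the infusion and no decline would be observed.

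**The case against.** The strongest objection is that little follows from this. PK is not among the outcomes in Section 2.2 and is absent from the proposed analyses in Section 9.0. Escalation rests on DLT counts. Nothing in the documents places the half-life near 1 h, and from 2 h upward the error is 2% or less. All of this stands and limits the point to a minor one.

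A second objection is that the upward direction depends on an undefined clock. That also stands: counted from infusion end, total AUC is too low and the log rule does not help.

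Three stronger readings are tempting, and the documents do not support them.

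- A reader might infer that clearance is understated. That needs a single-exponential decline and a sound K_el. With a distribution phase and a slope drawn from the 2-h and 4-h samples, AUC0-infinity can be too low and clearance too high, and changing the trapezoid rule does not cure it.
- A reader might infer that comparisons of exposure between doses are distorted, since Section 6.1.2 gives Cmax of about 90 and 200 µM at 2,300 and 3,000 mg/m² (200/90 = 2.22 for a dose ratio of 3,000/2,300 = 1.30). No such comparison is planned; Section 5.2.3 only tabulates, graphs and estimates. If those figures do reflect saturable elimination, the true decline lies between the straight and the log line, so the log rule would err low and neither rule is exact.
- A reader might infer that K_el will be regressed on raw concentrations. The plan does not say so, and most analysts would read a terminal rate constant as log-linear. This is a missing detail, not an error.

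**Conclusion.** The point holds in a limited form. If times run from the start of a 2-h infusion, the linear rule overstates AUC0-t. For first-order, one-compartment decline AUC0-4h is too high by about 17%, 7%, 2% and 0.5% at assumed half-lives of 0.5, 1, 2 and 4 h, so it is material only at about 1 h or less. The linear-up/log-down rule was closer in all the two-compartment cases above as well, though it did not remove the error. No direction can be claimed for clearance.

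On the same timing, a half-life of 2 h or more exposes a larger weakness: two samples carry K_el, t1/2, Cl, Vd and 36% or more of AUC0-infinity. The rule change does not touch that. The effect is confined to descriptive PK.

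**What to change.** In Section 5.2.3:

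- Replace the AUC rule with the *linear-up/log-down trapezoidal rule*: linear while concentrations rise, logarithmic while they fall.
- State that post-dose times are counted from the start of infusion or, if they are counted from the end, say that instead. Compute AUC on actual sampling times.
- As a clarification, define K_el by *linear regression of log concentration on time in the terminal phase*.
- Report AUC0-infinity, t1/2, Cl and Vd only where the samples support a terminal phase, and show the extrapolated share of AUC beside them.

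The 2-h duration (Tables 5-1, 5-2 and 6-1) and the pump rate in Section 7.5 must be reconciled by those responsible for dosing; this review takes no view on which is right.

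The PK changes are wording and reporting only, with the same samples and assay.
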